23.0 Appendix 3 Statistical analysis plan

Sample size and randomisation

We have assumed that a sample size of 3000 is feasible and that this is likely to be distributed as 750 in the "low response/no response" group and 2250 in the "normal response" group. We might then wish to estimate what difference between these two groups we could detect with 90% power. We have good estimates from previous studies over time in vulnerable populations and have therefore considered a range of infection and hospitalisation rates that might be plausible for this group. We have also considered the statistically most conservative option by setting the proportion at 50%.

In all cases, we can detect an absolute difference between groups of less than 10% and often less than 5% even for the rarer outcome of hospitalisation. These are consistent with a standardised effect sizes ranging from 0.15 to 0.36 for infection, which are consistent with small to moderate effects. The effect size for hospitalisation is less certain and ranges from 0.24 consistent with a small effect through to 1.33, a very large effect.

We consider this reassuring as it indicates that for a wide range of scenarios, we should have adequate power in the whole cohort for our primary outcome of infection and we may have power to detect a moderate effect for the rarer secondary outcome of hospitalisation, depending on the prevailing population rates and the variant of interest.

We will monitor all the assumptions that underlie these calculations at least monthly and will discuss monthly at our Trial Meeting Groups, if there are any concerns about power for key analyses.

Randomisation procedure

This is an observational cohort and participants will not be randomised. The cohort may be used in future to recruit to randomised trials and the process for selection and randomisation would be described accordingly in the associated trial protocol.

Statistical analysis considerations

Definition of analysis populations

CV groups are defined below and are derived in part from the QCOVID4 risk groups.

The Healthy Control (HC) group represent a population sampled from the PITCH Study (Protective immunity from T-cells in healthcare workers).

Baseline characteristics

At baseline the following characteristics will be described for the study cohort:

- Demographics (Age, BMI, self-reported ethnicity, sex, Index of Multiple Deprivation)

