For all participants, we will calculate the QCOVID risk score and explore whether this is associated with adverse outcome in this cohort. QCOVID was derived for hospitalisation and death as an outcome so we will explore this relationship in the first instance. However, we will also test whether QCOVID is valid for predicting our primary outcome of infection. The key outcomes in our cohort are binary so logistic regression will be used, with QCOVID risk score as the exposure variable. In line with the common protocol published for validation of the QCOVID algorithm (Kerr et al BMJ Open 2022) (but using the latest QCOVID4 score), Harrell's C statistic will be used to determine model discrimination and predicted probabilities of outcomes will be used to determine model calibration.

ii) Is the QCOVID4 score associated with anti-S titres in our cohort? (low/med/high and quantitative analysis)

We will quantify the relationship between QCOVID4 risk score and the anti-S titres using Pearson or Spearman's correlation, as appropriate to the distribution. We will also summarise the mean QCOVID score for each group of antibody results (none, low, normal) and use ANOVA to test for between group differences.

iii) Is the QCOVID4 score associated with T-cell responses in our cohort? (positive/negative and quantitative)

We will undertake the same analyses described in ii above for T-cell responses in relation to QCOVID4 risk score.

iv) Does the addition of serology measurements enhance QCOVID4 score?

Version: 2.0 26.11.2023 IRAS:325967

If QCOVID4 score shows good model discrimination and calibration with respect to adverse outcome or infection in our cohort, we will explore whether serology measurements improve the model. Serology measurements will be added to the logistic regression model and model fit diagnostics produced as per the common protocol (see i above). We will test these nested models to determine whether serology measurements significantly improve the model.

B) Identify additional laboratory methods to predict COVID-19 infection/hospitalisation if antibody testing fails to predict relevant clinical outcomes

Peripheral blood (and mucosal) samples will be stored, so that alternative assays can be performed to look for correlates of protection should blood anti-S IgG fail to stratify for COVID-19 risk. These will include:

- i) Antigen-specific T-cell response e.g. through IFNy ELISpot (Oxford, Southampton)

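### As written, QCOVID4 calibration would be judged on a logistic model refitted in this cohort, which says nothing about whether QCOVID4's own absolute risks are right

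*Protocol*

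**What the plan says.** Appendix 3 evaluates QCOVID4 under Exploratory Analyses. Part (i) calculates the score for every participant and notes that "QCOVID was derived for hospitalisation and death as an outcome". Hospitalisation and death are therefore examined first, and infection is tested as well. Because the key outcomes are binary, "logistic regression will be used, with QCOVID risk score as the exposure variable". The next sentence gives the performance measures. It opens "In line with the common protocol published for validation of the QCOVID algorithm", and then states that "Harrell's C statistic will be used to determine model discrimination" and that "predicted probabilities of outcomes will be used to determine model calibration".

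Part (iv) sets a condition: "If QCOVID4 score shows good model discrimination and calibration with respect to adverse outcome or infection in our cohort", the authors will explore whether serology improves the model. It continues: "Serology measurements will be added to the logistic regression model and model fit diagnostics produced as per the common protocol (see i above". The nested models are then compared. Nowhere does the text describe comparing QCOVID4's own predicted risks with the outcomes observed in this cohort.

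**The concern.** Validating a published risk score asks two things: does it rank people correctly, and are the absolute risks it gives correct in the new population? The second can only be answered with the risks the score itself produces. When the score is entered as an exposure in a new logistic regression, the intercept and coefficient are re-estimated from the study data. The predicted probabilities are then those of a recalibrated model, checked on the same data that recalibrated it.

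At stake is any statement that QCOVID4 is, or is not, well calibrated in clinically vulnerable people. The protocol names QCOVID4 among the alternative predictors if antibody testing fails (section 4.2, exploratory objective a), so such a statement would be read with interest. The calibration half of the condition in (iv) also depends on it.

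**Working it through.** The plan states no calibration figure, so there is none to reproduce.

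**Step 1: which model is assessed.** Part (i) fits a logistic regression with the score as exposure and then speaks of model calibration. Part (iv) adds serology to that regression and refers back to (i) for the diagnostics. Part (iv) also asks for calibration with respect to infection. The score was derived for hospitalisation and death and gives no infection risk of its own, so for infection the probabilities can only come from the refitted model. One sentence covers all outcomes.

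**Step 2: algebra.** Let y be the outcome, x the score, and p = 1/(1 + exp(−(a + b·x))), with a and b estimated by maximum likelihood. The score equations are

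- Σ(y − p) = 0
- Σ x(y − p) = 0

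The first makes expected events equal observed events (E/O = 1). Together they mean that regressing y on the fitted linear predictor a + b·x returns intercept 0 and slope 1 in the same data. With x = logit(QCOVID4 risk), these values stand where QCOVID4's own intercept and slope should be. Raw risk changes the shape of the fitted curve, and a grouped check or plot can pick that up. If the low/medium/high categories named in (i) enter as indicators, the model reproduces each category's observed proportion exactly.

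**Step 3: simulation.** The size is 3000, from the plan ("We have assumed that a sample size of 3000 is feasible"), with 500 replicates per scenario. Score distributions and miscalibration are assumptions, because the documents give none. The Hosmer-Lemeshow (HL) test, with 10 groups at the 5% level, illustrates a grouped check; the plan does not name it. Degrees of freedom were 10 for own risks and 8 for refitted ones.

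- A, odds 5 times too high: own logit risk has mean −2.2, SD 1; true logit = own − ln 5; event rate 3.4%.
- B, odds 5 times too low: mean −4, SD 1; true logit = own + ln 5; event rate 11.5%.
- C, risks too extreme: mean −2.2, SD 1.2; true logit = −1.5 + 0.4 × own; event rate 9.2%.
- D, correctly calibrated: mean −2.5, SD 1; event rate 10.6%.

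| | A | B | C | D |
|---|---|---|---|---|
| E/O, QCOVID4's own risks | 4.01 | 0.25 | 1.60 | 1.00 |
| Slope, own risks | 1.00 | 1.00 | 0.40 | 1.00 |
| HL rejects, own risks | 100% | 100% | 100% | 4.6% |
| E/O, refitted on logit(risk) | 1.00 | 1.00 | 1.00 | 1.00 |
| Slope, refitted on logit(risk) | 1.00 | 1.00 | 1.00 | 1.00 |
| HL rejects, refitted on logit(risk) | 6.4% | 4.8% | 3.6% | 4.8% |
| E/O, refitted on raw risk | 1.00 | 1.00 | 1.00 | 1.00 |
| HL rejects, refitted on raw risk | 27% | 100% | 38% | 93% |
| C statistic, own and refitted on logit(risk) | 0.755 | 0.748 | 0.632 | 0.750 |

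**Step 4: reading the table.** On the logit scale, the refitted check gives the same answer for a correct score as for one that is several-fold wrong. On the raw scale, the grouped test rejects more often for the correctly calibrated score (93%) than for A (27%) or C (38%). It is responding to functional form. The C statistic is the same for own and refitted risks, so it is sound but does not reveal miscalibration.

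**The case against.** The strongest reply is that the regression and the calibration check stand in separate sentences. The regression answers the question of association posed in (i). The calibration sentence refers to a published validation protocol and does not say whose probabilities are meant. QCOVID4 produces risks of its own, and that protocol may intend them. Its content is not available here, so this ambiguity stands. The wording of (iv), and the inclusion of infection, still point to the refitted model. If the other meaning was intended, one sentence settles it.

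A reader might infer more than the documents support:

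- That the check passes however badly QCOVID4 is calibrated. This is exact for E/O. The plan does not say on which scale the score enters, and with raw risk a grouped check can fail, though not because of QCOVID4's calibration.
- That the condition in (iv) cannot screen anything. Its discrimination half is unaffected and still works.
- That the serology comparison is compromised. The nested test remains valid whatever QCOVID4's absolute calibration.
- That the fault applies equally to infection. There refitting is unavoidable, because no native risk exists.

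It is also fair to say that the several-fold errors are assumed, and that 3000 exceeds the number who will test positive. HL rejection on own risks would therefore be less frequent in practice. The identities in Step 2 depend on neither.

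**Conclusion.** The point holds in a limited form. On the natural reading, the planned calibration check is made on a model refitted in this cohort. E/O = 1 is then guaranteed, and so is slope 1 when the score enters as logit(risk). Where a check could fail, it would fail through functional form. In neither case does it say whether QCOVID4's own absolute risks are right in clinically vulnerable people. In the assumed scenarios, E/O from 0.25 to 4.01 in QCOVID4's own risks appears as 1.00.

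The algebra needs no assumptions about this cohort. The reading of the text is an inference, qualified by the cited validation protocol that could not be consulted. The consequence is confined to an exploratory analysis: what may be claimed about QCOVID4 calibration, and the calibration half of the condition in (iv). The C statistic, the nested comparison and the primary result stand.

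**What to change.** Amend Appendix 3, Evaluation of QCOVID4 risk score, as follows.

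1. **Hospitalisation and death.** Assess QCOVID4's own predicted risk without refitting. Restrict this to participants who test positive, the population named in the title of the cited QCOVID4 reference (section 20.0, reference 4). Use the score's own time horizon, which the protocol does not give and should state. Report the observed/expected ratio, the calibration intercept and slope on logit(QCOVID4 risk), and a calibration plot.
2. **Part (iv).** Base the calibration condition, and any statement about QCOVID4 calibration, on item 1.
3. **Infection.** Report association and discrimination only, and label any refitted probabilities as recalibrated.
4. **Refitted model.** Keep it for association and for the nested comparison with serology, with logit(QCOVID4 risk) as the base term.

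If the cited validation protocol already prescribes item 1, say so explicitly.

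The score is already to be calculated for all participants, so no new score is needed. The work lies in the wording and in defining the tested-positive population and the horizon. The downside is that the calibration result may be less favourable, and it will be less precise because it rests on infected participants and few events.

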24.0 Appendix 4 Abbreviations

In full	Abbreviation
Adverse event	AE
Association of the British Pharmaceutical Industry	ABPI
British Society of Immunology	BSI
Case report form	CRF
Chronic Kidney Disease	CKD
Clinical Immunology Service	CIS
Coronavirus disease-2019	COVID-19
Clinically Vulnerable	CV
Dried Blood Spot	DBS
Estimated Glomerular Filtration rate	eGFR
Good Clinical Practice	GCP
Haematopoietic stem cell transplant	HSCT
Health care workers	HCW
Human Immunodeficiency Virus	HIV
Monoclonal gammopathy of undetermined	MGUS
significance	
Myelodysplastic syndrome	MDS
Myeloproliferative neoplasms	MPN
Nucleocapsid	N
Patient and Public Involvement	PPI
Research Ethics Committee	REC
Serious Adverse Events	SAEs
Severe acute respiratory syndrome coronavirus 2	SARS-CoV-2
Solid organ transplant	SOT
Spike	S
Trial Steering Committee	TSC
University of Birmingham	UoB
Variant of Concern	VOC

25.0 Appendix 5 Covid Severity Score

Patient Status	WHO	Proposed severity score STRAVINKSY for inf of hospital	Proposed severity sco acquired infection	
	WHO description	STRAVINSKY description	Score	
Uninfected	Uninfected		0	0
Ambulatory mild disease	Asymptomatic, viral RNA detected	Asymptomatic	1	Asymptomatic
	Symptomatic independent	Mild symptoms, no need for bedrest or assistance	2	Mild symptoms, no as
	Symptomatic, assistance needed	Symptoms that require bedrest or assistance	3	Symptoms that requir oxygen
Hospitalised moderate disease	Hospitalised, no oxygen therapy	Hospitalised, admitted for COVID, no oxygen**	4	Symptoms that requir oxygen
	Hospitalised oxygen by mask or nasal prongs	Hospitalised, admitted for COVID and required oxygen	5	Oxygen required for s
Hospitalised severe disease	Hospitalised, oxygen by NIV or high flow	Hospitalised, admitted for COVID and required oxygen	5	Oxygen required for s
	Intubation and mechanical ventilation pO ₂ /FI0 ² >150 or SpO ₂ /FI0 ² >200	Hospitalised on ITU for COVID	6	Transferred to ITU fo
	mechanical ventilation pO ₂ /FI0 ² <150 or SpO ₂ /FI0 ² <200 or vasopressors	Hospitalised on ITU for COVID	6	Transferred to ITU fo
	mechanical ventilation pO ₂ /FI0 ² <150 and vasopressors, dialysis or ECMO	Hospitalised on ITU for COVID	6	Transferred to ITU fo
Dead	Dead	Dead	7	Dead

WHO clinical progression scale

Patient State	Descriptor	Score
Uninfected	Uninfected; no viral RNA detected	0
Ambulatory mild disease	Asymptomatic; viral RNA detected	1
	Symptomatic; independent	2
	Symptomatic; assistance needed	3
Hospitalised: moderate disease	Hospitalised; no oxygen therapy*	4
	Hospitalised; oxygen by mask or nasal prongs	5
Hospitalised: severe diseases	Hospitalised; oxygen by NIV or high flow	6
	Intubation and mechanical ventilation, pO₂/FiO₂ ≥150 or SpO₂/FiO₂ ≥200	7
	Mechanical ventilation pO ₃ /FiO ₂ <150 (SpO ₃ /FiO ₃ <200) or vasopressors	8
	Mechanical ventilation pO ₃ /FiO ₂ <150 and vasopressors, dialysis, or ECMO	9
Dead	Dead	10

Follow up STRAVINSKY- Remote Patients

With the autumn 2023 booster vaccinations underway, we anticipate patients recruited into the STRAVINSKY study will now fall into the 3 categories below. *This may change again, pending government decisions on vaccinations, all changes will be communicated to sites before they are implemented in the database.*

Recruitment PRIOR to autumn 2023 booster AND if a participant is going to have an autumn 2023 vaccine AND has not yet had Autumn 2023 booster

Click "YES" to planning to have autumn 2023 booster on REDCap

Central Team will send two DBS cards with instructions for patient to return the second DBS card 28 days after autumn vaccination.

Local team – please reiterate temporal instructions to return 2nd DBS 4-10 weeks post vaccination

All patients to have a 3rd DBS, 6 months after the autumn 2023 vaccine date (date from patient access form will be used)

Recruitment after participant has had the autumn 2023 booster

Recruited - central team will send one DBS.

Local team – please reiterate that this should be filled in as soon as possible but a minimum of 28 days and ideally between 4 and 10 weeks post autumn 2023 booster.

All patients to have a 3rd DBS, 6 months after the autumn 2023 vaccine date (date from COVID history form will be used)

Participant chooses not to take up autumn 2023 booster

The above notification is based on most recent vaccination prior to Autumn 2023 and ticks "NO" to planning to have Autumn 2023 booster

Recruited - central team will send one DBS

Central team to send a 2nd DBS, 6 months from recruitment date (date of completed registration form will be used)

Follow up STRAVINSKY- Face to Face Visits

All patient visits due will be set as a notification on the database. If your patient is due to be booked into a clinic, you will receive a reminder two weeks before the due date.

Recruitment PRIOR to autumn 2023 booster AND if a participant is going to have an autumn 2023 vaccine AND has not yet had Autumn 2023 booster.

The above notification is based on most recent vaccination prior to Autumn 2023 and ticks "YES" to planning to have Autumn 2023 booster.

Recruited - Study team to take bloods and other tests as per the protocol Visit 1

Study team to arrange another visit 28 day after Autumn vaccination if they have clicked "yes" to having booster in Autumn 2023 Visit 3

All patients to have a Visit 6 months post autumn 2023 vaccine date (from patient access form) Visit 4

Recruitment after participant has had the autumn 2023 booster

Recruited - study team to arrange Visit as soon as possible but a minimum of 28 days and ideally between 4 and 10 weeks post autumn 2023 booster Visit 1*

Visit to be arranged 6 months after autumn 2023 booster (date from COVID history form) Visit 4

Participant is choosing not to take up autumn 2023 booster

The above notification is based on most recent vaccination prior to Autumn 2023 and ticks "NO" to planning to have Autumn 2023 booster

Recruited - Study team to take bloods and other tests as per the protocol Visit 1

Visit to be arranged at 6 months from recruitment date (use date of completed registration form) Visit 4

* Please note that the blood tube requirements for Visit 1 are slightly different to other visits. Regardless of when the participant is recruited, their first attendance or first DBS is considered Visit 1. This will ensure the correct tubes are collected.
